3.3.1.3 Laboratory data principles

Assessed values of the form ' $< x$ ' (below the lower limit of quantification [LLOQ]) or ' $> x$ ' (above the upper limit of quantification [ULoQ]) will be imputed as ' $x/2$ ' for ' $< x$ ' and ' x ' for ' $> x$ ' in the calculations of summary statistics but displayed as ' $< x$ ' or ' $> x$ ' in listings. The number of imputations will be summarised. Missing safety laboratory data will not be imputed.

3.3.1.4 Study Day

Study Day will be calculated from the randomisation date and will be used to show start/stop day of assessments and events. Day 1 is the day of randomisation, Day -1 is the day prior to the date of randomisation, there is no Day 0.

- If the date of the event is on or after the randomisation date, then:
 - Study Day = date of event – date of randomisation + 1.
- If the date of the event is prior to the randomisation date, then:
 - Study Day = date of event – date of randomisation.

3.3.1.5 Study periods

Study periods for Full Analysis Set (FAS)

Screening period

The screening period starts at the date of signed informed consent and ends at the day before randomisation. For subjects enrolled but not randomised, the enrolment period ends at last visit.

Planned treatment period

The follow-up time for the Planned treatment period will be calculated from randomisation and to the earliest of day of visit 11 (if subject attended visit 11, otherwise day 343 will be used), date of withdrawal of consent or date of death. If withdrawal of consent or death did not occur, it

will be calculated from randomisation and to the earliest of day of visit 11 (if subject attended visit 11, otherwise day 343 will be used) or the last study visit.

Study periods for Safety Analysis Set (SAS)

Pre-treatment period

The pre-treatment period starts at the date of signed informed consent and ends before the date and timepoint of first dose of IP.

On-treatment period

The follow-up time for the On-treatment period will be calculated from the date of the first dose of IP and to the earliest of 14 days after last dose, date of withdrawal of consent or date of death. If withdrawal of consent or death did not occur, it will be calculated from the date of the first dose of IP and to the earliest of 14 days after last dose of study drug or the last study visit..

On-study period

The follow-up time for the On-study period will be calculated from the date of the first dose of IP and to the earliest date of withdrawal of consent or date of death. If withdrawal of consent or death did not occur, it will be calculated from the date of the first dose of IP and to the last study visit.

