- g One PK sample will be collected pre-dose from all participants. In a subset of participants (approximately 20%), 3 additional post-dose samples will be collected at Visit 6. Visit 6 sample collection times are: pre-dose, and 0.5 to 1.5 h, 1.5 to 3 h and > 3 h post-dose, with a minimum of 1 hour between the post-dose sampling occasions. Once approximately 20% of participants have been tested, no further participants would need this additional post dose sampling. For participants who are discontinued from investigational product due to rash, a PK sample should be collected at the discontinuation visit.
- h CCI [REDACTED]
- i CCI [REDACTED]
- j Only for participants who discontinue investigational product due to rash or skin reaction: blood and urine sample for exploratory metabolite analysis should also be collected at the EDV.
- k Screening echocardiogram can be performed on a different day if it is not possible to be done on the screening visit day due to scheduling purposes but must be as soon after the screening visit as possible ie, within 1-2 days in order to allow for results to be back prior to randomisation. For the echocardiogram at Visit 8 and Visit 9, if due to scheduling purposes the echocardiogram cannot be performed on the same day as the clinic visit, the echocardiogram should be performed at the earliest opportunity and within 7 days of the scheduled visit.
- l The first dose of study intervention will be administered in clinic on the day of randomisation after completing all pre-dose procedures. Participants will receive study intervention at the site on visit days and at home between visits for a total of 48 weeks.
- m AEs will be collected from the first dose (the only exception is related to the pre-dose orthostatic test at Visit 3: if orthostatic hypotension is confirmed, it should be reported as an AE, and symptoms related to the measurement of orthostatic vitals if present should also be reported as an AE). SAEs will be collected from signing of the ICF.

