8.3.1 Time Period and Frequency for Collecting AE and SAE Information

Adverse events will be collected from the time of the first dose throughout the treatment period and including the follow-up period (final follow up is Visit 12 for Part A and Visit 8 for Part B). The only exception is related to the pre-dose orthostatic test at Visit 3: if orthostatic hypotension is confirmed, it should be reported as an AE, and symptoms related to the measurement of orthostatic vitals if present should also be reported as an AE.

SAEs will be recorded from the time of signing of the informed consent form.

If the investigator becomes aware of an SAE with a suspected causal relationship to the investigational medicinal product that occurs after the end of the clinical study in a participant treated by him or her, the investigator shall, without undue delay, report the SAE to the sponsor.

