4.6.2 Adverse Events

4.6.2.1 Definitions and Derivations

Adverse event will be assigned to the analysis period based on the onset date, as defined in Section 3.3.1.5.

Adverse events will be classified by SOC and PT and coded using Medical Dictionary for Regulatory Activities (MedDRA).

Risk for an event will be estimated using KM% estimates. Comparisons of risk for an event between the treatment groups will be estimated by HRs with 95% CIs based on a Cox regression model with a factor for treatment group, and difference in KM%. A subjects first event that occurs during the On-treatment or On-study period, respectively, will be included in the analysis. All subjects who are event free for the given AE (or AE category) will be censored according to the definitions in Sections 3.3.1.5 and 3.3.1.8.

Any AE

Defined as an AE reported with an onset date within the defined period.

Any SAE

Defined as an AE reported as serious, irrespective of outcome.

SAEs with outcome death

Defined as an AE with reported outcome as 'Fatal', there may be more than one AE with outcome death for a subject. The onset date of the AE determines the analysis period, irrespective of date of death.

AEs leading to discontinuation of IP

Defined as an AE with action taken IP reported as drug permanently discontinued. The onset date of the AE determines the analysis period, irrespective of date of discontinuation of IP.

AEs possibly related to IP

Defined as an AE that is reported as "reasonable possibility AE caused by IP". If this evaluation is missing, it will be counted as an AE possibly related to IP.

AEs by maximum intensity

AEs will be classified by the reported maximum intensity, "Mild", "Moderate" and "Severe". If this maximum intensity evaluation is missing, it will be counted as "Severe".

Adverse events of special interest

The following two groups of adverse events are Adverse events of special interest (AEoSI):

- Infections: will be identified by the SOC "Infections and infestations".
 - The pathogen specific High level group term (HLGT) "Fungal infectious disorders".
- Skin reactions, including maculopapular rash:
 - Skin reactions/rashes considered maculopapular (described as macules/papules under the morphology/appearance question).
 - Skin reactions/rashes not considered maculopapular (not described as macules/papules under the morphology/appearance question).

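### Orthostatic hypotension confirmed before the first dose counts as a Day 1 on-treatment and on-study AE, which dilutes the hazard ratio for that term and for related symptoms

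*SAP*

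**What the plan says.** **Which pre-dose events become AEs.** AEs are collected from the first dose. Protocol 8.3.1 then adds: "The only exception is related to the pre-dose orthostatic test at Visit 3". Confirmed orthostatic hypotension at that test, and symptoms related to the measurement, are to be reported. Footnote m of the Part A schedule of activities repeats the rule. Under Protocol 8.2.2.1 and Table 7, an asymptomatic case is confirmed only if 2 of 2 or 2 of 3 test sequences are positive. One sequence suffices when there are symptoms.

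**When dosing happens.** The Part A schedule (Protocol 1.3) says: "The first dose of study intervention will be administered in clinic on the day of randomisation after completing all pre-dose procedures". The pre-dose test and the first dose therefore share a calendar date.

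**How the SAP defines the periods (3.3.1.5).**
- On-treatment: "The follow-up time for the On-treatment period will be calculated from the date of the first dose of IP".
- On-study: "The follow-up time for the On-study period will be calculated from the date of the first dose of IP".
- Pre-treatment: it "ends before the date and timepoint of first dose of IP".

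**How AEs are counted (SAP 4.6.2.1).** "Adverse event will be assigned to the analysis period based on the onset date, as defined in Section 3.3.1.5". Then: "A subjects first event that occurs during the On-treatment or On-study period, respectively, will be included in the analysis". SAP 4.6.2.2 reports Kaplan-Meier percentages at 16 and 48 weeks, with differences and hazard ratios for the active groups against placebo.

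**The concern.** An event found before the first tablet is swallowed cannot be an effect of the drug. Under the date-only rule it is nevertheless tabulated as on-treatment and on-study. Because only the first event per subject counts, a subject who is positive before dosing can contribute no later orthostatic hypotension event, not even one found at the scheduled Week 12 test. The term affected is the one that the orthostatic test was designed to pick up.

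The same event also meets the Pre-treatment definition, because that definition alone still refers to a clock time. The three definitions in SAP 3.3.1.5 thus disagree about what happens on Day 1.

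**Working it through.** **Does the event enter, and does anything remove it?**
1. It is reportable: Protocol 8.3.1, "pre-dose orthostatic test at Visit 3: if orthostatic hypotension is confirmed, it should be reported as an AE".
2. Its onset date is the date of first dose (Protocol 1.3).
3. SAP 3.3.1.5 and 4.6.2.1 place it in both safety periods. By SAP 3.3.1.8, time at risk is onset date minus first-dose date plus 1, which is Day 1.
4. Protocol 9.4.3 leaves the Part A definition of treatment-emergent events to the SAP. SAP 4.6.2 gives no such definition for AEs and relies on the periods alone, so nothing filters the event out.

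**Size.** The plan states no rate for orthostatic hypotension, so there is no figure to reproduce and every rate below is an assumption. Let x be the share of each arm with a pre-dose event, and F the risk of a post-dose first event among the rest.

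- Counted risk = x + (1 − x)F
- Counted difference = (1 − x)(F_active − F_placebo)
- Counted risk ratio = [x + (1 − x)F_active] / [x + (1 − x)F_placebo]

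With F = 2% on active and 1% on placebo:

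| x | Active | Placebo | Risk ratio | Difference (points) |
|---|---|---|---|---|
| 0 | 2.00% | 1.00% | 2.0 | 1.0 |
| 2% | 0.02 + 0.98×0.02 = 3.96% | 0.02 + 0.98×0.01 = 2.98% | 1.33 | 0.98 |
| 5% | 0.05 + 0.95×0.02 = 6.90% | 0.05 + 0.95×0.01 = 5.95% | 1.16 | 0.95 |
| 10% | 0.10 + 0.90×0.02 = 11.80% | 0.10 + 0.90×0.01 = 10.90% | 1.08 | 0.90 |

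The SAP plans a Cox hazard ratio rather than a risk ratio, so that was computed as well. The method was the large-sample solution of the Cox score equation, with the pre-dose events tied on Day 1, Efron handling of ties, constant hazard afterwards, and pooled active to placebo 2:1. With assumed post-dose risks by Week 48 of 10% on active and 5% on placebo:

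| x | Hazard ratio | Kaplan-Meier difference (points) |
|---|---|---|
| 0 | 2.05 | 5.0 |
| 2% | 1.75 | 4.9 |
| 5% | 1.51 | 4.75 |
| 10% | 1.33 | 4.5 |
| 20% | 1.17 | 4.0 |

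The two measures behave differently: the ratio is pulled strongly toward 1, while the difference keeps the fraction (1 − x) of its size. The difference does become noisier. With 220 placebo and 440 pooled active subjects (660 randomised 1:1:1), x = 10% means about 22 and 44 subjects with a pre-dose event. The difference divided by its standard error then falls from 2.44 to 1.49 in the 10% versus 5% case.

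**The case against.** **The drug question is answered elsewhere.** SAP 4.6.8 analyses the orthostatic test directly. It has a post-first-dose view limited to subjects without a pre-dose fall in blood pressure, and a Week 12 view. Its category for falls reported as AEs takes only AEs after the first dose on that day or on the day of the Week 12 measurement. A listing flags AEs within 3 hours after the first dose. This is substantial mitigation and it stands. However, the Day 1 post-dose view covers only subjects randomised before 12 August 2022, and none of it corrects the AE tables, Kaplan-Meier percentages or hazard ratios of SAP 4.6.2.

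**Reach and consequence are limited.** Non-serious AEs before dosing on Day 1 arise only from this one exception. Orthostatic hypotension is not among the AEs of special interest. Safety is descriptive, without p-values (Protocol 9.4.3), and every AE is listed. All of this stands. It makes the point minor, but a descriptive hazard ratio should still not contain events that precede exposure.

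**Date-only was deliberate.** The SAP amendment history records dropping the dose timepoint as a simplification. That explains the rule. It does not reconcile it with the protocol's pre-dose exception or with the clock time left in the Pre-treatment definition.

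**Stronger readings that a reader might infer, and that the documents do not support:**
- *A drug effect would be masked.* What happens is dilution of a ratio. The planned Kaplan-Meier difference shrinks little.
- *Any positive pre-dose test becomes an AE.* Without symptoms, confirmation is required, so x is lower than the raw positive-test rate.
- *The event is counted twice.* The period definitions overlap, but the AE tabulations use only the On-treatment and On-study periods (SAP 4.6), so no planned AE table counts it in a second place through the Pre-treatment period.
- *The arms carry equal numbers of pre-dose events.* Randomisation gives equality only in expectation. A chance imbalance could move the contrast either way.

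**Conclusion.** The point holds, and it is minor. On the current text, confirmed orthostatic hypotension at the Visit 3 pre-dose test, and symptoms related to that test, are analysed as Day 1 first events in both safety periods and displace later events of the same term. In expectation this moves the hazard ratio for those terms toward 1. The Kaplan-Meier difference is reduced only by the factor (1 − pre-dose share), and the effect on broad categories such as any AE is small.

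The direction follows from the rules together with randomisation. The size rests entirely on assumed rates, because the documents supply none. Dilution would be greater if the subjects who are positive before dosing are also those most prone to a later drug-related event. The inconsistency between the Pre-treatment definition and the other two needs correcting whatever the rates turn out to be.

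**What to change.** In SAP 3.3.1.5 and 4.6.2.1, state that AEs arising from the Visit 3 pre-dose orthostatic test are assigned to the Pre-treatment period, excluded from the On-treatment and On-study AE analyses, and listed separately. Where both the AE start time and the first-dose time are recorded, apply the same rule to any Day 1 AE with onset before the first dose. Align the three period definitions so that a Day 1 event belongs on one side of the first dose only.

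The link to the pre-dose test should be the main rule and the clock-time comparison the addition. AE start time is collected (Protocol 8.3.2), but the in-clinic dose time is recorded only where applicable (Protocol 6.4). Preferred term and date alone will not do for subjects randomised before 12 August 2022. They could also have a post-dose test on Day 1, so the pre-dose and post-dose results must be told apart.

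The cost is a short SAP edit, one programming filter and one listing, plus reliance on a visit flag or on Day 1 timing.

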7.3 Lost to Follow up

A participant will be considered lost to follow-up if he or she repeatedly fails to return for scheduled visits and is unable to be contacted by the study site and vital status not found in publicly available sources at the end of the study.

The following actions must be taken if a participant fails to return to the clinic for a required study visit:

- The site must attempt to contact the participant and reschedule the missed visit as soon as possible and counsel the participant on the importance of maintaining the assigned visit schedule and ascertain whether or not the participant wishes to and/or should continue in the study.
- Before a participant is deemed lost to follow up, the investigator or designee must make every effort to regain contact with the participant (where possible, 3 telephone calls and, if necessary, a certified letter to the participant's last known mailing address or local equivalent methods). These contact attempts should be documented in the participant's medical record.
- Should the participant continue to be unreachable, he/she will be considered to have withdrawn from the study.
- Site personnel, or an independent third party, will attempt to collect the vital status of the participant within legal and ethical boundaries for all participants randomised, including those who did not get investigational product. Public sources may be searched for vital status information. If vital status is determined as deceased, this will be documented and the participant will not be considered lost to follow-up. Sponsor personnel will not be involved in any attempts to collect vital status information.

Discontinuation of specific sites or of the study as a whole are handled as part of Appendix A.

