3.3.1.8 Time at risk and censoring

If a subject has an event with onset day during the study period being analysed (see Section 3.3.1.5), it will be included in the analysis. For subjects with an event, the time at risk will be derived as

- *Event onset date – date of randomisation + 1 for FAS*
- *Event onset date – date of first date of IP + 1 for SAS*

For event-free subjects, the time at risk will be derived based on the study period being analysed, see the definition in Section 3.3.1.5. Event-free subjects are censored on the last day of the study period.

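### SAP follow-up after the last visit depends on outcome: participants found dead are followed to death, while those alive are censored at the last visit

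*SAP*

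**What the plan says.** SAP 3.3.1.5 gives the On-study period two possible ends. It runs "to the earliest date of withdrawal of consent or date of death. If withdrawal of consent or death did not occur", then "it will be calculated from the date of the first dose of IP and to the last study visit". There is no upper day limit. The Planned treatment period, used for the time-to-cardiovascular-event analysis (SAP 4.2.16.2), has the same structure with a cap. With a death, it ends at the earliest of Visit 11 (Day 343 if Visit 11 was not attended), consent withdrawal and death. Without death or withdrawal, the last study visit takes their place: "if subject attended visit 11, otherwise day 343 will be used) or the last study visit".

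SAP 3.3.1.8 counts an event if its onset lies in the period, and adds: "Event-free subjects are censored on the last day of the study period".

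Protocol 7.3 provides that site staff or a third party "will attempt to collect the vital status of the participant within legal and ethical boundaries for all participants randomised". It adds "Public sources may be searched for vital status information", and "If vital status is determined as deceased, this will be documented and the participant will not be considered lost to follow-up". No SAP rule uses a last-known-alive or vital-status date.

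**The concern.** Whether time after the last visit counts as time at risk is decided by what happens later. Deaths after the last visit enter the numerator. The matching time of comparable people known to be alive is left out of the denominator. A non-fatal event learned of after the last visit, such as a heart failure hospitalisation, can likewise count for someone who later dies but not for someone who survives. This sits badly with the treatment-policy handling in SAP 4.2.16.1 and SAP 4.6, which is implemented by including all available data.

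The outputs at stake are:
- Kaplan-Meier percentages, event rates and hazard ratios for the cardiovascular composite and its components, including cardiovascular and all-cause death.
- The On-study analysis of fatal SAEs, but only where the AE began after the last visit, because SAP 4.6.2.1 assigns these by AE onset.

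**Working it through.** **The rule applied to two people.** Both last attend on Day 100 and neither withdraws consent.

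| Status found by the 7.3 search | End of On-study and Planned treatment periods | Contribution to the death analysis |
|---|---|---|
| Died on Day 300 | Day 300 | Event, with 200 days at risk after the last visit |
| Alive at study end | Day 100 | Censored, with no time after the last visit |

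Consent withdrawers are treated alike, because their period ends at withdrawal whatever follows. The rule for undated deaths in SAP 3.3.1.2 moves a death to the last visit date but still counts it, so it does not repair the asymmetry.

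**Inputs for the size.** The documents give no figure that rests on this rule, so there is none to reproduce.
- Death rate λ: 50 to 75 per 1000 patient-years (Protocol 2.2).
- Horizon T: Day 343, so T = 343/365.25 = 0.939 years.
- Share p who stop attending: an assumption, 3% to 9.1%. The upper value is 60/660, the share without complete safety data in Protocol 9.2, as if all of them stopped attending.
- Base case: stopping time uniform, all later deaths found, hazard unchanged after stopping.

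**Approximation by hand.** By time t a fraction p·t/T has stopped. Of these, the rule keeps in the risk set only those who will die before T. The apparent hazard is therefore

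λ / (1 − (p·t/T)·exp(−λ(T−t))),

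which averages to about λ(1 + p/2) over the period.

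| λ per year | p | True: 1 − exp(−λT) | SAP rule: 1 − exp(−λT(1 + p/2)) | Relative inflation |
|---|---|---|---|---|
| 0.050 | 3% | 4.59% | 4.65% | 1.4% |
| 0.050 | 9.1% | 4.59% | 4.79% | 4.4% |
| 0.075 | 3% | 6.80% | 6.90% | 1.4% |
| 0.075 | 9.1% | 6.80% | 7.10% | 4.4% |

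**Simulation on the Part A visit schedule** (1,000,000 participants per scenario, KM mortality at Day 343, truth to SAP rule):
- 50 per 1000: 4.57 to 4.65% at 3% loss; 4.56 to 4.81% at 9.1%.
- 75 per 1000: 6.74 to 6.86% at 3% loss; 6.79 to 7.16% at 9.1%.
- Rates per 1000 patient-years at 9.1% loss: 49.6 to 52.4, and 74.9 to 79.0.
- Crude percentages are the same under both rules (4.56% and 6.79% at 9.1% loss). With no loss, the KM values are identical too.

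The simulated shifts slightly exceed the hand values because survivors are censored at the last scheduled visit before they stop.

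**Direction** (75 per 1000, 9.1% loss):

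| Hazard after stopping | Late deaths found | True KM | SAP rule |
|---|---|---|---|
| unchanged | 25% | 6.78% | 6.93% |
| unchanged | 50% | 6.75% | 6.97% |
| ×2 | 50% | 7.04% | 7.13% |
| ×3 | 100% | 7.37% | 7.74% |
| ×3 | 25% | 7.32% | 7.04% |

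**Comparison between arms.** With equal loss and ascertainment, the factor 1 + p/2 applies to both arms and nearly cancels. If loss were 9% against 3%, with no drug effect, the rate ratio would be about 1.045/1.015 = 1.03. That contrast is hypothetical.

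**The case against.** The strongest reply is that the effect is negligible. At 3% loss about 20 of 660 people stop, with about half a year left each. That is 10 patient-years, or 0.5 to 0.75 deaths in all of Part A (1.5 to 2.2 at 9%). With 220 per arm the standard error of KM mortality is about 1.5 to 1.7 points, well above a shift of 0.1 to 0.4. The composite is exploratory and outside the testing hierarchy of SAP 3.3.4, and Protocol 9.4.3 makes safety descriptive, without p-values. All of this stands and limits the weight of the point. It does not justify the rule, because this is a systematic error that wording can remove.

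Three stronger readings might be inferred, and the documents do not support them.
- *The bias is always upward.* Protocol 7.3 promises only an attempt to find vital status, and the last row above shows a reversal.
- *Discontinuation for rash will distort the hazard ratio.* Protocol 7.1 keeps participants who stop drug in scheduled visits, so stopping does not itself shorten On-study follow-up. The On-treatment period is capped at last dose plus 14 days. Nothing suggests different loss by arm.
- *The data for the repair are already held.* Protocol 7.3 says that a death is documented. It does not say that a confirmed-alive date is recorded.

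The SAP also leaves the last study visit undefined. If telephone contacts count, the gap shrinks, but a public-records check is not a visit.

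**Conclusion.** The point holds as a bounded one. The SAP makes the end of the On-study and Planned treatment periods depend on outcome for participants who stop attending without withdrawing consent, and no other SAP rule corrects this. If most late deaths are found, KM mortality and event rates are too high by about 1% to 5% relative (0.1 to 0.4 points) for 3% to 9% loss. The size rests on the protocol's background death rate, uniform loss and full ascertainment. The 9% figure is an upper illustration, since the 60 without complete safety data would also include consent withdrawals. The sign can reverse when few late deaths are found and hazard rises after loss. Hazard ratios should move little. The primary tests and crude counts are untouched. The change is worth making because the stated estimator is biased and the repair is small.

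**What to change.** In SAP 3.3.1.5 and 3.3.1.8, define an end of follow-up that does not depend on outcome.

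- **Death.** Censor event-free participants at the last date known alive, including the vital-status date from Protocol 7.3, capped at the planned end of the period. Add such a cap to the On-study period. Record the confirmed-alive date alongside deaths.
- **No confirmed-alive date recorded.** Leave deaths found only by a vital-status search out of the time-to-event estimate and list them separately. Otherwise the asymmetry returns.
- **Non-fatal events.** End the period for everyone, including those who later die, at the last contact at which events were ascertained, whether visit, telephone or modified follow-up under Protocol 7.2.
- **Composite.** Apply one of these rules to survivors and non-survivors alike.

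The cost is a SAP wording change, one derived date and recording of the alive-confirmation date.
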